#### **5.4.7. Vital Signs**

For all participants, weight and height (and BMI) at baseline will be summarized using descriptive statistics.

No other presentations of vital signs are planned.

#### **5.4.8. Follow-up of Safety data**

Median, minimum, maximum, and interquartile range of the follow-up time from first study vaccination for each of the vaccination groups (except the mixed schedule group) of Section 5.4.4 will be provided for the FAS. Separate tables will be produced for the combined double-blind, open-label active, and open-label passive phase and for the combined double-blind and open-label active phase.

For the tables covering the combined double-blind and open-label active phase:

The follow-up time for an individual who initially received placebo will be censored at i) the date of receipt of Ad26.COV2.S or a vaccination given outside of the study, ii) the date of study discontinuation, iii) the date of study site approval for PA7, or iv) the date of database cutoff, whichever occurred first. The follow-up time for an individual whose first active vaccination was Ad26.COV2.S will be censored at i) the date of receipt of a vaccination given outside of the study, ii) the date of study discontinuation, iii) the date of study site approval for PA7, or iv) the date of database cutoff, whichever occurred first. For the vaccination groups that received first an mRNA or non-mRNA vaccination and then an Ad26.COV2.S vaccination, the follow-up will start from the first Ad26.COV2.S vaccination and will be censored at i) the date of receipt of a vaccination given outside of the study, ii) the date of study discontinuation, iii) the date of study site approval for PA7, or iv) the date of database cutoff, whichever occurred first.

For the tables covering the combined double-blind, open-label active phase, and open-label passive phase the follow-up time is not censored at the date of study site approval of PA7.

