#### **5.4.2. Study Phases**

A baseline (or reference) value will be defined as the value of the last available assessment prior to the first study vaccination on Day 1.

The safety analyses will present all results by study phase (see Section [5.4.3](#)).

Study day or relative day is defined as follows:

- Study Day = visit date – date of Day 1 + 1; if visit date  $\geq$  date of Day 1 (date of first vaccination).
- Study Day = visit date – date of Day 1; if visit date  $<$  date of Day 1 (date of first vaccination).

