#### **5.4.4. Vaccination groups**

All safety analyses will be tabulated by vaccination group according to the *as treated* principle. The COVID-19 vaccinations received outside of the study are considered as well. Participants can be present in more than 1 vaccination group as described below. Safety data by vaccination group will be analyzed descriptively.

The following vaccination groups will be presented:

A. Layout 1a:

1. Placebo

All participants who received as first vaccination a placebo injection. All safety data will be reported here until the participant receives an active COVID-19 vaccination (Ad26.COV2.S or outside vaccination).

2. Ad26.COV2.S

All participants who received as first active COVID-19 vaccination Ad26.COV2.S until the participant receives an outside COVID-19 vaccination. This includes participants who initially received placebo and subsequently received Ad26.COV2.S, however only the safety data after the Ad26.COV2.S vaccination until the participant receives an outside

COVID-19 vaccination (if applicable) will be presented here. The safety data of participants who received 2 or more Ad26.COV2.S vaccinations will be presented by post-dose 1, post-dose 2, etc.

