#### **5.4.6.2. Analysis of Adverse Events**

The number and percentage of participants with at least one particular AE will be tabulated with exact 95% CI, when appropriate. Additionally the incidence rate will also be derived as number of participants with at least one particular AE per 100 person years of follow-up. Unsolicited AEs will be summarized by System Organ Class and Preferred Term.

Denominator for the percentages is the number of participants in the considered population and phase for a certain vaccination group (incidence per 100 participants/phase). Denominator for the incidence rates is the number of person years in the considered population and phase for a certain vaccination group (incidence per 100 person years/phase).

For unsolicited AEs, the following tables will be provided: summary table (including SAEs, SAEs related to study vaccine, MAAEs, MAAEs leading to study discontinuation, MAAEs related to study vaccine, AEs with fatal outcome, AEs related to study vaccine with fatal outcome, AEs related to study vaccine leading to study discontinuation, and AEs leading to study discontinuation), all events, AEs at least grade 3, AEs related to study vaccination, AEs at least grade 3 and related to study vaccination, AEs leading to study discontinuation, SAEs related to study vaccination, SAE (overall, associated with COVID, not associated with COVID), MAAE, selected AEs of interest, fatal AEs, and AESI.

Listings and/or participant narratives will be provided as appropriate, for those participants who die, discontinue study due to an AE, or experience a serious AE.

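### Section 5.4.8 gives no Ad26.COV2.S start date for cross-over participants, so their placebo time also counts as Ad26.COV2.S follow-up

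*SAP*

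**What the plan says.** Section 5.4.8 describes the safety follow-up tables. The general rule is to report summary statistics, among them the "interquartile range of the follow-up time from first study vaccination for each of the vaccination groups"; participants on a mixed schedule are left out. Three rules follow, one per type of participant:

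- Placebo: "The follow-up time for an individual who initially received placebo will be censored at i) the date of receipt of Ad26.COV2.S". An outside vaccine, discontinuation, PA7 site approval or database cut-off also ends it, if earlier.
- Ad26.COV2.S: "The follow-up time for an individual whose first active vaccination was Ad26.COV2.S will be censored at i) the date of receipt of a vaccination". The vaccination meant is an outside one, and the other end dates are those of the placebo rule. No start is given.
- Outside mRNA or non-mRNA vaccine followed by Ad26.COV2.S: "the follow-up will start from the first Ad26.COV2.S vaccination and will be censored at" the same dates. Only here is a start date stated.

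A second set of tables, which adds the passive phase, uses the same rules without censoring at PA7 site approval.

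Section 5.4.4 (Layout 1a) places in the Ad26.COV2.S group everyone whose first active vaccine was Ad26.COV2.S, including those who began on placebo. For the latter, it says, "only the safety data after the Ad26.COV2.S vaccination until the participant receives an outside" vaccine belongs there.

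**The concern.** The general rule and the group definition use different starting points for the same people. Whoever drafted 5.4.8 saw that one group needed its own start date and supplied it. The Ad26.COV2.S group needs one just as much, because it takes in the cross-over participants, and it received only censoring rules.

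The figure at stake is the length of observation after Ad26.COV2.S, which readers use to judge how far a long-term safety statement reaches. If the table is programmed as written, blinded placebo time is presented as time under observation after the vaccine.

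**Working it through.** The SAP states no follow-up duration or person-time for this table, so there is no figure to reproduce. The check compares the rules and then illustrates the size.

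**1. Is placebo a study vaccination?** Yes, in this SAP.
- Section 5.4.2 anchors study day at the "date of Day 1 (date of first vaccination"), which is the placebo injection for someone randomised to placebo.
- Section 5.4.3 has to say that placebo given after an active vaccine is not counted as a study vaccination. That exception is needed only if placebo otherwise counts.
- Section 5.2.5 lists follow-up from first study vaccination and follow-up from last Ad26.COV2.S vaccination as two different measures.

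**2. One cross-over participant.** Assume placebo on Day 1, Ad26.COV2.S 0.5 year later, and PA7 site approval 1.0 year after that.
- Placebo rule: 0.5 year.
- Ad26.COV2.S rule as written, from first study vaccination: 0.5 + 1.0 = 1.5 years.
- Sum: 2.0 years for a person observed for 1.5. The placebo half-year is counted twice.
- Section 5.4.4 shows this person's events in the Ad26.COV2.S group for 1.0 year only.

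**3. Effect on the group mean or total.** Inputs: about 15,000 per group (Table 2); and, as assumptions, cross-over share x = 0.5 to 1.0, placebo time p = 0.25 to 0.75 year, and time after cross-over a = 0.75 to 1.0 year. Participants randomised to Ad26.COV2.S contribute p + a each.

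- Person-years consistent with 5.4.4: 15,000(p + a) + 15,000·x·a
- Person-years as written in 5.4.8: 15,000(p + a) + 15,000·x·(p + a)
- Relative excess: x·p / [(p + a) + x·a]

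Lowest case (x = 0.5, p = 0.25, a = 1.0): 18,750 + 7,500 = 26,250 against 18,750 + 9,375 = 28,125, an excess of 7.1%. Highest case (x = 1.0, p = 0.75, a = 0.75): 22,500 + 11,250 = 33,750 against 22,500 + 22,500 = 45,000, an excess of 33.3%.

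| x | p 0.25, a 0.75 | p 0.25, a 1.0 | p 0.5, a 0.75 | p 0.5, a 1.0 | p 0.75, a 0.75 | p 0.75, a 1.0 |
|---|---|---|---|---|---|---|
| 0.5 | 9.1% | 7.1% | 15.4% | 12.5% | 20.0% | 16.7% |
| 0.8 | 12.5% | 9.8% | 21.6% | 17.4% | 28.6% | 23.5% |
| 1.0 | 14.3% | 11.1% | 25.0% | 20.0% | 33.3% | 27.3% |

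For the cross-over participants alone the excess is p/a, from 0.25/1.0 = 25% to 0.75/0.75 = 100%. The number of participants is the same under both rules, so the percentages apply equally to the mean and the total. In the tables that add the passive phase, the excess in years is the same but a is longer, so the relative excess is smaller.

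**4. Effect on the printed statistics.** Lengthening some participants' follow-up can only raise the median, quartiles, minimum and maximum or leave them unchanged. How far each moves depends on the distribution of dates, which the SAP does not give. In the two-value picture above, cross-over participants are x/(1 + x) = 33% to 50% of the group. The lower quartile then rises by the whole placebo interval, from a to p + a. The median need not move while those randomised to Ad26.COV2.S are the majority. With real, spread-out dates the median would generally move too. The maximum changes only if a cross-over participant has the longest follow-up.

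**5. Do adverse event rates use this follow-up time?** No. Section 5.4.6.2 says: "Denominator for the incidence rates is the number of person years in the considered population and phase" for a vaccination group. Section 5.4.3 builds separate post-dose periods for placebo and active injections and restarts the numbering at 1 when only placebo came before. Placebo time does not enter the Ad26.COV2.S denominators.

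**The case against.** The strongest reply is that 5.4.8 summarises the groups as defined in 5.4.4, where a cross-over participant's Ad26.COV2.S data begin at that dose. It also censors placebo starters when they receive Ad26.COV2.S. A programmer who reads both sections would probably start at the right dose, so this is a wording gap that another section largely resolves. That stands as to scale: it is a small correction to a descriptive table. It does not remove the contradiction, because 5.4.8 states a start for every group and replaces it for only one.

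A reader might infer two stronger points, and the SAP supports neither.

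- *Safety rates are diluted by placebo time.* They are not, for the reason in step 5. A total such as 15,000 × 0.25 = 3,750 or 15,000 × 0.5 = 7,500 misplaced person-years is also not a figure that 5.4.8 prints. It is an upper bound as well, since Table 2 notes that newly enrolled Group 2 participants receive no placebo.
- *Adverse event rates are wrong because time runs on after the first event.* Section 5.4.6.2 openly defines the rate as "number of participants with at least one particular AE per 100 person years of follow-up", over all person-time in the phase. That is a recognised crude rate. The passive-phase efficacy rates in 5.3 do not stop at the event either. With a constant hazard over a 1.5-year phase, the crude rate is low by 0.75% at 1 per 100 person-years: (1 − e^(−0.015))/1.5 = 0.00993 against 0.01. At 10 per 100 it is low by 7.1%, but the long phase holds mainly serious and special-interest events, because general MAAEs are collected only to 6 months after last vaccination. Changing this rate is a matter of preference.

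**Conclusion.** The point holds for the follow-up summary and nowhere else. As written, 5.4.8 counts cross-over participants' placebo time in two groups, contradicts 5.4.4 and overstates follow-up after Ad26.COV2.S. The excess is about 7-33% of the group mean or total, assuming 50-100% cross-over, 0.25-0.75 year on placebo and 0.75-1.0 year afterwards. None of these three inputs is in the SAP, and early exits to outside vaccines are not modelled. The direction of the error is certain; the shift in the median is not quantified. Adverse event percentages and incidence rates are unaffected.

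**What to change.** In 5.4.8, state that follow-up for the Ad26.COV2.S group starts at the first Ad26.COV2.S vaccination, in both sets of tables (with and without the passive phase). The placebo rule already ends at the first active vaccine and can stay. Table titles should name each group's start rather than first study vaccination. The cost is one sentence and a small programming change. The downside is that the stated follow-up after Ad26.COV2.S becomes shorter.

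No change of denominator is needed in 5.4.6.2. At most, label that rate as a crude rate per total person-time in the phase.

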## 5.5. Immunogenicity

### 5.5.1. Immunogenicity (Double-Blind Phase)

Blood will be collected from all participants for humoral immunogenicity assessments before the 1st vaccination (for subjects enrolled during the double-blind phase of the study), at the open-label unblinding visit (prior to vaccination, where applicable), at the booster vaccination visit (prior to vaccination) and also at Day 71 (visit 5) or Week 32 (visit 7).

During a COVID-19 episode, blood will be collected on COVID-19 Day 3-5 and on COVID-19 Day 29 and immunogenicity assessments may be performed, including the assays summarized in [Table 7](#).

No immunogenicity analyses will be performed for the combined double-blind and open-label active phase. Immunogenicity analyses for the double-blind phase have already been reported.

**Table 7: Overview of Immunogenicity assessments**

Humoral Assays	Purpose
Supportive of Secondary Objectives	
SARS-CoV-2 binding antibodies to S protein (ELISA)	Analysis of antibodies binding to SARS-CoV-2 S protein
SARS-CoV-2 seroconversion based on antibodies to N protein (ELISA and/or SARS-CoV-2 immunoglobulin assay)	Analysis of antibodies binding to SARS-CoV-2 N protein
Supportive of Exploratory Objectives	
SARS-CoV-2 neutralization (VNA)	Analysis of neutralizing antibodies to the wild-type or variant virus, and/or pseudovirion expressing S protein
SARS-CoV-2 binding antibodies to S protein (MSD)	Analysis of antibodies binding to SARS-CoV-2 S protein (different than the assays supportive of the secondary objectives) and the receptor-binding domain (RBD) of SARS-CoV-2 S protein
Functional and molecular antibody characterization	Analysis of antibody characteristics including, but not limited to, avidity, Fc-mediated viral clearance, Fc characteristics, Ig subclass, IgG isotype, antibody glycosylation, and assessment of antibody repertoire
Adenovirus neutralization (VNA)	Adenovirus neutralization assay to evaluate neutralizing antibody responses against the Ad26 vector
Binding antibodies to other coronaviruses (MSD)	Analysis of antibodies binding to coronaviruses other than SARS-CoV-2

Ad26 = adenovirus type 26; ELISA = enzyme-linked immunosorbent assay; Fc = crystallizable fragment; Ig(G) = immunoglobulin (G); MSD = Meso Scale Discovery; N = nucleocapsid; RBD = receptor-binding domain; S = spike; SARS-CoV-2 = severe acute respiratory syndrome coronavirus-2; VNA = virus neutralization assay.

\*N-serology used for assessment of asymptomatic SARS-CoV-2 assessment, rather than immunogenicity of Ad26.COV2.S as SARS-CoV-2 nucleocapsid is not included as antigen in the vaccine

### 5.5.2. Immunogenicity (Open-Label Passive Phase)

During the open-label passive phase (following study site approval of PA6 and PA7), for participants who are not part of the Immunogenicity Subset, no samples for assessment of immunogenicity will be taken. For a total of approximately 200 participants from the on-active

group of the Immunogenicity Subset (double-blind phase), blood will be collected for analysis of humoral immune responses at Week 32 (visit 7), Week 60 (visit 8), Week 86 (visit 9), and Week 112 (visit 10).

The analysis of immunogenicity will use the PPI set.

Humoral immunogenicity data will be analyzed according to the as-treated principle by vaccine regimen (2-doses of Ad26.COV2.S), by vaccine regimen and participant seropositivity status at screening, by vaccine regimen and age and comorbidity (with/without) strata, and by vaccine regimen and region.

Correlate of immunity will not be assessed in this study.

#### **5.5.2.1. Parameters**

The following humoral immune responses are measured by immunogenicity against the insert using humoral immune responses, including titers of neutralizing antibodies and S-ELISA titers, functional and molecular antibody characterization and RBD antibodies and N-ELISA positivity. Immunogenicity against the vector may be explored using an adenovirus neutralization assay to assess neutralizing antibody responses against the vector.

#### **5.5.2.2. Handling of Missing and/or Unquantifiable Immune Response Data**

Missing immune response data will not be imputed.

- Values will be imputed based on the type of analysis. For the calculation of the geometric mean titer, values below LLOQ will be imputed to LLOQ/2. While for the calculation of the fold increase from baseline, values below LLOQ will be imputed to LLOQ. The LLOQ values per assay are available in the database.

Values above the upper limit of quantification (ULOQ) will be imputed with the ULOQ for both the calculation of geometric mean and fold increase from baseline.

In case a LOD is reported, the same rules as described above for LLOQ are applied.

#### **5.5.2.3. Immune Response Analysis**

No formal hypothesis on immunogenicity will be tested.

#### **5.5.2.4. Immunogenicity Against the Insert:**

##### **5.5.2.4.1. Humoral assays**

For VNA (both wild-type virus and pseudovirion expressing S protein, as available), S-ELISA, and ADCP assays, the following results will be calculated: N, geometric meana§ and corresponding

---

a calculate the mean and corresponding 95% CI of the  $\log_{10}$  transformed values, back-transform this mean [i.e.  $10^{\text{mean}}$ ] and CI [i.e.  $10^{\text{CI}}$ ].

95% CI of the actual values and fold increases from baseline will be tabulated and graphically presented.

For the calculation of the geometric mean and its corresponding 95% CI, the arithmetic mean and its corresponding 95% CI are calculated on the  $\log_{10}$  transformed values. These values are back transformed to provide the geometric mean and its corresponding 95% CI.

For wild type, pseudovirion VNA, S-ELISA, and ADCP separately:

- A sample will be considered positive if its value is strictly greater than the LLOQ ( $>\text{LLOQ}$ ).
- Responder definition. A post-baseline sample will be considered a responder if at least one of the following conditions is satisfied:
  - The baseline sample value is less than or equal to the LLOQ ( $\leq\text{LLOQ}$ ) and the post-baseline sample is strictly greater than the LLOQ ( $>\text{LLOQ}$ )
  - The baseline sample value is strictly greater than the LLOQ ( $>\text{LLOQ}$ ) and the post-baseline sample value represents an at least 4-fold ( $\geq 4$ -fold) increase from the baseline sample value.

Actual values are tabulated and shown as box plots with the corresponding geometric mean, 95% CI per time point and minimum and maximum are shown for each assay. For the Immunogenicity Subset actual values are tabulated and shown as dot plots with dots for participant values, and the corresponding geometric mean and 95% CI per time point for each assay.

In addition, geometric mean titer (GMT) plots over time, combining the regimens in one graph (without individual participant dots) will also be generated.

Participant profiles of the actual values over time will be graphically presented for Covid-19 cases.

Correlation plots between humoral assay results will be performed for selected time points.

In graphs, original values will be displayed on a  $\log_{10}$  scale.

Further details may be provided in the DPS. For the **N-serology** the proportion of participants that are positive will be tabulated.

#### **5.5.2.5. Immunogenicity Against the Vector**

For immunogenicity against the Ad26 vector backbone (Adenovirus neutralization by neutralization assay), the following statistics will be calculated if assessment is performed: geometric mean and corresponding 95% CI of the actual values, and number and percentage of participants with a positive sample.

Correlation plots with the Adeno assays versus the assays against the inserts will be provided for the most important time points.

## **5.6. Interim Analyses**

No interim analyses are planned for the open-label phase of the study.

### **5.6.1. Independent Data Monitoring Committee (IDMC)**

The study will be formally monitored by an Independent Data Monitoring Committee (IDMC, also known as a Data Safety Monitoring Board or DSMB). In general, the IDMC will monitor safety data on a regular basis to ensure the continuing safety of the participants. Enrollment (if applicable) will not be paused during regular safety reviews. The IDMC will review unblinded data. The IDMC responsibilities, authorities, and procedures will be documented in the IDMC Charter.

Since the safety of Ad26.COV2.S has been established, in February 2022 the IDMC agreed that there was no need to continue reviewing safety data for this study.

### **5.6.2. Clinical Severity Adjudication Committee**

The Clinical Severity Adjudication Committee will review all cases in the study, except for cases already adjudicated as severe, as a supplement to the algorithm described in the double-blind SAP, as well as those requiring medical intervention (such as a composite endpoint of hospitalization, ICU admission, mechanical ventilation, and ECMO, linked to objective measures such as decreased oxygenation, X-ray or CT findings), including onset of cases, taking into account all available relevant information at the time of adjudication (as explained in the charter). Depending on an algorithmic selection the cases will be sent for adjudication on a case by case basis or on a sample approach, as explained in the double-blind SAP. Readjudication will occur if new information becomes available. The last adjudication for a given case will determine the status of the case for analysis.

As of 8 July 2022, no further adjudication was performed and no efficacy endpoints will be created based on the CSAC assessment for the analysis of the open-label phase of the study.

## 6. SUPPORTING DOCUMENTATION

### 6.1. Appendix 1 List of Abbreviations

ADaM	Analysis Data Model
AE	adverse event
AESI	Adverse event of special interest
ATC	Anatomical Therapeutic Chemical classification system
BMI	body mass index
CD4	cluster of differentiation 4
CDC	Center for Disease Control and Prevention
CI	confidence interval
COVID-19	coronavirus disease-2019
CRF	case report form
CTP	clinical trial protocol
DD	drug dictionary
DPS	Data presentation specifications
eCOA	electronic clinical outcome assessment
ECMO	extracorporeal membrane oxygenation
ELISA	enzyme-linked immunosorbent assay
FAS	full analysis set
FDA	Food and Drug Administration
GMR	geometric mean ratio
GMT	Geometric Mean Titer
ICF	informed consent form
IDMC	Independent Data Monitoring Committee
LLOD	lower limit of detection
LLOQ	lower limit of quantification
MAAE	medically-attended adverse event
MPD	Major Protocol Deviation
PP	per protocol efficacy analysis set
PPI	per protocol immunogenicity analysis set
PRAC	Pharmacovigilance Risk Assessment Committee
RBD	receptor-binding domain
RNA	ribonucleic acid
RT-PCR	reverse-transcriptase polymerase chain reaction
SAE	serious adverse event
SAP	statistical analysis plan
SD	standard deviation
SDTM	Study Data Tabulation Model
SMQ	Standardized MedDRA Query
ULOQ	upper limit of quantification
US	United States
VE	vaccine efficacy
VNA	virus neutralization assay
vp	virus particle
WHO	World Health Organization

